2.2.1.2 Key Secondary Analysis

The key secondary endpoint is the number of days to achieve discharge from hospital or readiness for discharge (NRD), whichever occurs first.

The FAS will be used to test the key secondary efficacy endpoint. See Section 1.4 for explanation of how twins will be handled in this analysis.

For the key secondary endpoint, the following hypothesis will be tested:

- H₀: The distribution of the number of days to NRD is the same in the treated and the placebo groups.
- H₁: The distribution of the number of days to NRD differs in the treated and the placebo groups.

where NRD = number of days to discharge (or readiness for discharge) from the hospital.

To maintain the overall study-wide two-sided Type I error rate at 0.05, a hierarchically ordered testing procedure, described in section 1.7, will be used. The testing of the key secondary endpoint will be by the van Elteren test, stratified by gestational age group and region (North America, Europe, and Israel) with a threshold for statistical significance of P<0.05. The average rank will be used for tied NRD values.

The Hodges—Lehmann estimator will be used to estimate the treatment differences (NTRA-2112 dose minus placebo) in days and their 95% confidence intervals.

2.2.1.3 Handling Missing Ranks for the Primary and Key Secondary Endpoints

Confidential Page 24 of 40

Statistical Analysis Plan V1.3 SAP Date: 06APR2018

2.2.1.3.2 Ranks for NEC and Death of Subjects

Infants who experience NEC (Necrotizing Enterocolitis) will be assigned ranks of NFE according to censoring times of 29 days and infants who die will be assigned ranks of NFE according to censoring times of 30 days. The individual ranks among subjects experiencing NEC and the individual ranks among subjects who die will be handled according to Section 1.3.3.

Since it can take significantly longer than 28 days to be discharged or being ready to be discharged, infants who experience NEC (Necrotizing Enterocolitis) will be assigned ranks of NRD according to censoring times of 181 days and infants who die will be assigned ranks of NRD according to censoring times of 182 days. The individual ranks among subjects experiencing NEC and the individual ranks among subjects who die will be handled according to Section 1.3.3.

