1.3.3 Sample Size and Statistical Power Considerations

Presentation of sample size is based on the hypothesis that NFE in either treatment group is shorter than in the placebo group. Based on limited historical data (Phase 2), the

Confidential Page 14 of 40

conservative mean is 8.0 days for the placebo group and 6.6 days for each of the 2 active dose groups. This assumes a standard deviation of 3.5 days for each group.

The analysis will be based on a nonparametric test. The NFEs for each infant in the FAS will be ranked from shortest time (the best outcome) to longest time. Infants who do not achieve full enteral feeding and also experience necrotizing enterocolitis (NEC) will be assigned the next set of ranks; all the infants experiencing NEC will be ranked in terms of their time to NEC (the earlier the worse) and will be assigned ranks one greater than the rank of the longest time to achieve NFEs. All infants who do not achieve full enteral feeding and die will be assigned the next set of ranks, again with the earliest deaths assigned the largest (i.e. worst) rank. Thus, each infant who has achieved EN or who has died or suffered NEC will have a recorded rank.

Randomization will be stratified by center and by gestational age group. The statistical analysis will stratify the infants by gestational age group and region (North America, Europe, and Israel), but not by center. Because the analysis will be based on ranks, a van Elteren test will be used to compare NTRA-2112 to placebo. To calculate sample size, an independent groups t-test for 85% power to account for the reduced power of the non-parametric test was used (i.e., expect that a t-test with 85% power to have at least 80% power when the van Elteren test is applied). A two-side 5% test will be used to compare each active dose to placebo. These calculations give N = 115 infants per group. To account for the reduction in power caused by potential missing data, the sample size was increased to 130 per group or a total sample size of 390

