• Survival ("time-to-event") analysis: a stratified log rank test will be performed to compare time-to-FEF (the first day of Full External Feeding). In this analysis, infants who experience NEC will be assigned censoring times of 29 days and infants who die will be assigned censoring times of 30 days. Any other infants who withdraw from the study early will be considered censored at the day of their last participation in the study (unless they have already achieved FEF in which case they will not be censored).

This time to event analysis will be reported for the time to FEF as the *first* of 3 consecutive days and again as the *third* of 3 consecutive days of enteral feeding.

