2.2.1.5 Sensitivity Analysis: The Second (Born) Twin

The second twin is the one who is assigned to the same treatment group as the first (born) randomized twin.

The following analyses will be performed on FAS to include the second twin.

One analysis will repeat test the primary and key secondary endpoints replacing the first-randomized twin by the second twin.

Another analysis will be a hierarchical mixed model that includes both twins in a way that accounts for the possible correlation between them. For the mixed effects model, the dependent variable will be the number of days, the independent variable is the treatment group, with gestation age group and the region (North America, Europe, and Israel) as two class covariates. A twin effect will be included in the model as a random cluster effect. For each singleton, the cluster has one subject, and for each twin the cluster will have two subjects. This random cluster effect is used to model the correlation within each twin-pair under the compound symmetry covariance structure.

Confidential Page 26 of 40

Statistical Analysis Plan V1.3 SAP Date: 06APR2018

For infants who experience NEC (Necrotizing Enterocolitis) or death, their ranks will be assigned in the same way as described in Section 2.2.1.3.2.

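### The public SAP gives two rules for an infant who reaches full feeding and later has NEC or dies: the observed number of days is kept under Section 1.3.3 and replaced by Day 29 or 30 under Section 2.2.1.3.2

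*SAP*

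**What the plan says.** SAP Section 1.3.3 ranks infants by NFE and places NEC and then death behind the achievers. Both groups are limited to infants who never reached full enteral feeding (FEF): "Infants who do not achieve full enteral feeding and also experience necrotizing enterocolitis (NEC) will be assigned the next set of ranks" and "All infants who do not achieve full enteral feeding and die will be assigned the next set of ranks".

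SAP Section 2.2.1.3.2 states the rule again without that limit: "Infants who experience NEC (Necrotizing Enterocolitis) will be assigned ranks of NFE according to censoring times of 29 days". Deaths are placed at 30 days in the same sentence. No time window is given. It then refers back: "The individual ranks among subjects experiencing NEC and the individual ranks among subjects who die will be handled according to Section 1.3.3".

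Three sensitivity analyses follow the second form:

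- Section 2.2.1.4 (log-rank): "infants who experience NEC will be assigned censoring times of 29 days and infants who die will be assigned censoring times of 30 days". An exception follows, "unless they have already achieved FEF in which case they will not be censored", but it belongs to the sentence about other infants who withdraw early.
- Section 2.2.1.5 (second twin): "For infants who experience NEC (Necrotizing Enterocolitis) or death, their ranks will be assigned in the same way" as in 2.2.1.3.2.
- Section 2.2.1.7 (tie-breaking): NEC and death are set to Day 29 and Day 30. Infants who missed the feeding criterion are listed separately, censored at Day 28.

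Protocol Section 12.3 makes the NEC rank conditional on not reaching enteral feeding but gives the death rank to all infants who die. Protocol Section 12.4 says the SAP prevails where the two differ.

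**The concern.** The two SAP sections disagree about who enters the NEC and death groups. The reference from 2.2.1.3.2 to 1.3.3 covers the order of infants within those groups, so it does not settle membership.

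Infants can have NEC or die after reaching full feeding. The planning means are 6.6 and 8.0 days and treatment runs to Day 28, so a typical infant has weeks at risk after reaching the endpoint. Under SAP Section 2 the study is unblinded after the last 3-month corrected-age visit, so later events will also be in the database.

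At stake is which infants count as failures on the primary endpoint. If the question is first noticed after unblinding, the answer becomes a choice made with the data in view. The futility analysis in SAP Section 3.1 uses the same endpoint values, so the rule is needed before that transfer.

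**Working it through.** **1. The two rules side by side**

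| Infant | Section 1.3.3 | Section 2.2.1.3.2 as worded |
|---|---|---|
| No FEF, then NEC or death | behind all achievers | Day 29 / Day 30 |
| FEF on Day 8, later NEC | keeps 8 | Day 29 |
| FEF on Day 8, later death | keeps 8 | Day 30 |

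Only the last two rows differ. In one simulated comparison of 115 against 115, recoding a single such infant moved it from rank 151 to rank 230 of 230.

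**2. The plan's own sample size**

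Inputs from SAP 1.3.3: means 8.0 and 6.6 (difference 1.4), SD 3.5, two-sided 5%, 85% power by t-test. The normal approximation gives

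n = 2(1.960 + 1.036)² × 3.5² / 1.4² = 2 × 8.98 × 6.25 ≈ 112.2, so 113 per arm.

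The exact t calculation gives 114. The SAP's 115 is reproduced and is used below.

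**3. Power under each rule**

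Each setting has 20,000 simulated trials of 115 per arm. NFE is normal, rounded to whole days and limited to 1–28. An assumed 3% per arm are non-achievers coded 29 or 30. The test is an unstratified, tie-corrected Wilcoxon; a win is z < −1.96 in favour of active. The same data are analysed with and without recoding post-FEF NEC to Day 29. The post-FEF rates are assumptions, because the documents give none.

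| Post-FEF rate, both arms | Power, 1.3.3 | Power, 2.2.1.3.2 | Loss (points) | Opposite decisions |
|---|---|---|---|---|
| 0.5% | 78.5% | 77.8% | 0.7 | 2.9% |
| 1% | 78.6% | 76.9% | 1.7 | 4.7% |
| 2% | 78.9% | 75.7% | 3.2 | 7.1% |
| 4% | 78.8% | 71.7% | 7.1 | 11.1% |
| 6% | 78.8% | 67.8% | 11.0 | 15.3% |

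With gamma-distributed NFE (same means and SD) power starts near 87% and the losses are 0.9, 1.3, 2.9, 6.0 and 9.6 points.

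| Active / placebo rate | Power, 1.3.3 | Power, 2.2.1.3.2 |
|---|---|---|
| 2% / 1% | 78.8% | 72.0% |
| 1% / 2% | 79.2% | 80.3% |
| 3% / 1% | 78.7% | 66.1% |
| 1% / 3% | 78.7% | 82.5% |

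With no treatment effect and equal rates of 1%, 2% and 6%, two-sided rejection is 4.82%, 4.86% and 4.84% under 1.3.3, and 4.79%, 4.83% and 5.04% under 2.2.1.3.2.

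**4. Worked example**

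Take 115 normal quantiles per arm, rounded to days, and recode k infants with NFE 8 to 29. Then z = (W − E)/√V, where W is the active rank sum, E = 115 × 231/2 = 13,282.5, and V is the tie-corrected variance.

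| Observed difference | Recoded infants | p |
|---|---|---|
| 1.4 days | none | 0.0034 (z = −2.93) |
| 1.4 days | 2 active | 0.0070 |
| 1.4 days | 5 active | 0.0186 |
| 1.4 days | 8 active | 0.0444 |
| 1.4 days | 9 active | 0.0580 |
| 1.0 day | none | 0.0355 (z = −2.10) |
| 1.0 day | 1 active | 0.0468 |
| 1.0 day | 2 active | 0.0610 |
| 1.0 day | 2 placebo | 0.0226 |

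At the planned difference it takes nine of 115 infants (9/115 = 7.8%), all on active, to lose significance. At 1.0 day it takes two.

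**The case against.** The strongest reply is that only one rule was meant. Section 2.2.1.3.2 stands under the heading "Handling Missing Ranks for the Primary and Key Secondary Endpoints", and an infant with an observed Day 8 has no missing rank. Censoring time is an odd term for an observed event. Section 3.1 treats NEC and death as reasons why a primary value is missing. Read literally, a death close to 24 months corrected age would overwrite a Day 8 result, which looks like shorthand. The opening of 2.2.1.3 and all of 2.2.1.3.1 are absent from the public copy and may state the condition; their absence is not a fault of the plan.

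Most of this stands as evidence of intent, and no claim is made here about which rule the sponsor will apply. It does not remove the conflict in the visible text. Sections 2.2.1.4 and 2.2.1.7 repeat the unconditional wording outside that heading. The exception for infants already at FEF shows that the authors could write the condition, yet they attached it only to other withdrawals. The protocol does not decide the matter either.

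The objection on size also stands in part. Every event rate is assumed, and the simulation omits the van Elteren stratification. At 0.5% to 1% the loss is under 2 points. The 1.0-day example starts near the threshold, where many small changes would cross 0.05.

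**Conclusion.** The concern holds. As worded in the public SAP, Section 2.2.1.3.2 replaces an observed NFE after later NEC or death, while Section 1.3.3 keeps it. The first is the wrong rule if followed literally, and it bears on the primary endpoint.

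If post-FEF events are rare and balanced the effect is small. It becomes material at rates of about 4% or more, or when the arms differ, and an imbalance can move power either way. The stated sample size is unaffected and no Type I inflation is claimed. These sizes rest on the planning means and SD, 115 per arm, an assumed 3% of non-achievers and assumed post-FEF rates. This should be fixed; confidence is medium because part of Section 2.2.1.3 cannot be seen.

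**What to change.** Before the interim data transfer and before unblinding:

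1. Use one membership rule in SAP Sections 1.3.3, 2.2.1.3.2, 2.2.1.4, 2.2.1.5 and 2.2.1.7. The natural choice is the explicit one in 1.3.3: Day 29 or Day 30 only for infants with NEC or death who do not reach FEF, with any observed NFE kept.
2. State the time window within which NEC, death and FEF count. Section 1.3.3 gives none, so this is the sponsor's decision.
3. Record in SAP Section 4 the difference from the protocol's wording for deaths.
4. Run the unconditional rule as a labelled sensitivity analysis.
5. Check the similar wording for the other days-to-event endpoints in Section 2.2.2 and for the discharge endpoint in 2.2.1.3.2 (Days 181 and 182). An FEF condition does not settle how to treat NEC followed by discharge, so the discharge endpoint needs its own statement.

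If the unseen text of 2.2.1.3 or 2.2.1.3.1 already contains the condition, repeating it in 2.2.1.3.2, 2.2.1.4 and 2.2.1.7 settles who enters the NEC and death groups for NFE.

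For NFE the cost is one sentence repeated in the listed sections, one line in Section 4 and one programming condition. No new data are needed.

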12.3. Sample Size Considerations

Presentation of sample size is based on the hypothesis that NFE in either treatment group is shorter than in the placebo group. Based on limited historical data (phase 2), the conservative mean is 8.0 days for the placebo group and 6.6 days for each of the 2 active dose groups. This assumes a standard deviation of 3.5 days for each group.

The analysis will be based on a nonparametric test. The NFEs for each infant in the FAS will be ranked from shortest time (the best outcome) to longest time. Infants who do not achieve EN because they experience NEC will be assigned the next set of ranks; all the infants experiencing NEC will be ranked in terms of their time to NEC (the earlier the worse) and will be assigned ranks one greater than the rank of the longest time to achieve NFEs. All infants who die will be assigned the next set of ranks, again with the earliest deaths assigned the worst rank. Thus, each infant who has achieved EN or who has died or suffered NEC will have an observed rank.

Study Infants will be randomized by center and by gestational age group. The statistical analysis will stratify the infants by gestational age group and region (United States and Europe), but not by center. Because the analysis will be based on ranks, a Van Elteren test will be used to compare NTRA-2112 to placebo. To calculate sample size, an independent groups t-test for 85% power to account for the reduced power of the non-parametric test was used (i.e., expect that a t-test with 85% power to have at least 80% when the Van Elteren test is applied). A 2.5% significance level to account for 2 dose comparisons to placebo was used. These calculations give N = 136 infants per group. To account for the reduction in power caused by potential missing data, the sample size was increased to 150 per group or a total sample size of 450.

Note: The sample size provided in this section relates only to those *infants included in the FAS*; however, the total number of infants treated with NTRA or placebo may be as high as 530, depending on how many of the infants in the study are pairs of twins. As described above, the FAS will include only the first born infant in a participating pair of twins. The second born sibling will be included in safety analyses and some supplementary efficacy analyses.

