2.2.2 Other Secondary Endpoints

The following other secondary endpoints will be analyzed on FAS only.

- Growth velocity (g/kg/day) at 6, 8, and 10 days, the last day of treatment (or Day 28), day of discharge, 3-month follow-up, 12-month follow-up, and 24-month follow up
- Change in Z-score at 6, 8 and 10 days, the last day of treatment (or Day 28), day of discharge, 3-month follow-up, 12-month follow-up, and 24-month follow up from initiation of treatment
- Gain in body weight at 6, 8, and 10 days, the last day of treatment (or Day 28), day of discharge, 3-month follow-up, 12-month follow-up, and 24-month follow up

Confidential Page 27 of 40

• Number and percentage of infants reaching full enteral feeding within 6, 8, and 10 days from initiation of treatment.

- Total number of days receiving parenteral nutrition
- Number of days to 120Kcal/kg/day
- Number of days to wean-off PN

For the continuous variables (growth velocity, z-score, body weight), ANCOVA analysis will be performed at each time point of interest, including treatment, the stratification factors of gestation age and region (North America, Europe, and Israel) as class variables, and the baseline values as a continuous covariate, the estimated treatment differences (NTRA-2112 minus placebo), 95% confidence intervals, and P-values will be provided.

For the variable of number of day to a given event, the van Elteren test stratified for gestation age and region will be performed. The average score will be used for the ties. Infants who experience NEC (Necrotizing Enterocolitis) and infants who die will be assigned the second worst and the worst ranks. The individual ranks among subjects experiencing NEC and the individual ranks among subjects who die will be handled according to Section 1.3.3.

For percent of infants reaching full external feeding, Cochran-Mantel-Haenszel (CMH) test stratified for gestation age and region will be performed.

Statistical testing of these other secondary endpoints will be considered exploratory and will not control for Type I error rate inflation.

No imputation will be performed for the missing values for the other secondary endpoints.

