4 SUMMARY OF MAJOR CHANGES IN THE PLANNED ANALYSES

The PP set is defined differently from the protocol, but the difference is not considered to be major. The approach described in the protocol of using methods that separate the reasons for noncompliance from the effect of study drug (e.g. Robins, 1989) will not be followed. Instead, the more common approach of defining a PP set based on study compliance will be adopted. PP analysis will only be supportive of the primary intention-to-treat analysis based on the FAS.

The treatment difference between two NTRA-2112 doses will be estimated for the primary endpoint, key secondary endpoint, exploratory secondary endpoint, and other endpoints.

The Bonferroni correction was described in the protocol for testing the primary and the key secondary endpoints simultaneously for each dose level. Nutrinia believe that insulin as a growth factor will have effect with both doses. We expect that there is an opportunity for exploring higher dose that may yield a more favorable clinical effect than the lower dose that was used in the phase 2. Thus for that reason, a hierarchical approach is now being implemented in the analysis. This procedure is described in Section 1.7 of this SAP to allow testing the primary endpoint, then secondary endpoint for the high dose first, then for the low dose while maintaining the type 1 error rate of 5% overall.

The sample size was re-calculated in Section 1.3.3 due to the change in the testing procedure stated above.

Section 2.2.1.3.2 was modified to allow longer time, up to 180 days, to observe the actual time for discharge or being ready to be discharged (NRD).

Section 2.2.1.7 was added for a sensitivity analysis using the baseline enteral feeding volume to break the tied NFE ranking.

Section 2.2.1.8 was added for a summary of number and percent of infants who achieve the complete and partial enteral feeding success for each treatment.

The reporting periods for AE reporting have been further defined in Section 2.3.2.1.

Section 3.1. The timing of the sample size re-estimation relevant to the futility analysis is further clarified. The conditional power is raised from 20% to 35%. Based on the conditional power and the totality of the clinical data available at the futility analysis, the DMC will recommend to continue or discontinue one or both dose arms. The sponsor will consider increasing the total sample size up to 450 patients based on the sample size

Confidential Page 37 of 40

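### Read literally, the SAP's NEC and death ranks for NRD can replace an observed day of discharge or readiness, making the key secondary test an undeclared composite

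*SAP*

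**What the plan says.** SAP 2.2.1.2 defines NRD as days to discharge or readiness for discharge, whichever is first. Its null hypothesis is "The distribution of the number of days to NRD is the same in the treated and the placebo groups". The test is a stratified van Elteren test at two-sided 0.05, with a Hodges–Lehmann difference in days.

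SAP 2.2.1.3.2 then states that "infants who experience NEC (Necrotizing Enterocolitis) will be assigned ranks of NRD according to censoring times of 181 days" and that "infants who die will be assigned ranks of NRD according to censoring times of 182 days". It adds: "The individual ranks among subjects experiencing NEC and the individual ranks among subjects who die will be handled according to Section 1.3.3". Section 1.3.3 orders NEC infants by time to NEC, and deaths by time of death, with earlier being worse. Its own entry condition is "Infants who do not achieve full enteral feeding and also experience necrotizing enterocolitis (NEC) will be assigned the next set of ranks". The protocol's counterpart (12.3) is also about feeding: "Infants who do not achieve EN because they experience NEC will be assigned the next set of ranks".

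SAP Section 4 explains the long horizon: "Section 2.2.1.3.2 was modified to allow longer time, up to 180 days, to observe the actual time for discharge". Protocol 12.1.1 gives special treatment (there, exclusion) only to infants who do not reach NRD because of death or complications.

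For the other time-to-event endpoints, SAP 2.2.2 says: "Infants who experience NEC (Necrotizing Enterocolitis) and infants who die will be assigned the second worst and the worst ranks". In SAP 1.7, NRD for the high dose is step 2 of the fixed sequence. If it fails, testing stops before either low-dose test.

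**The concern.** NEC does not prevent NRD from being observed. An infant can have NEC, recover, and go home or meet the readiness criteria well within 180 days. The rule in 2.2.1.3.2 has no exception for that infant: a rank in the Day 181 block replaces the observed day, and the position within the block depends on when NEC began rather than on length of stay.

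The death rule has the same gap. It has no time limit, and by SAP Section 2 the study is unblinded only after the last 3-month corrected-age visit. A death after discharge home could therefore turn an observed NRD into 182.

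Two things are at stake. First, the reported result would answer a different question from the stated hypothesis, and two programmers could derive different NRD ranks from the same data. Second, power may be lost at step 2, where a failure also stops the low-dose primary and key secondary tests.

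**Working it through.** **1. The texts side by side**

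| Place | Whom the special rule covers |
|---|---|
| Protocol 12.1.1 (NRD) | only infants not reaching NRD because of death or complications |
| Protocol 12.3 (NFE) | infants who fail to reach enteral feeding because of NEC; infants who die |
| SAP 1.3.3 (NFE) | NEC or death without full enteral feeding |
| SAP 2.2.1.3.2 (NRD) | NEC, or death; no further condition |
| SAP 2.2.2 (other time-to-event endpoints) | NEC, or death; no further condition |

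SAP 2.2.1.3.2 cites 1.3.3 only for the order among NEC infants and among deaths. If the entry condition of 1.3.3 is imported as well, the outcome depends on the feeding window:

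- *Full feeding at any time.* Readiness itself requires full feeding, so NEC infants who become ready keep their observed day.
- *Full feeding within the treatment period* (the window SAP 2.2.1.7 uses for NFE). An infant whose feeding NEC delays past Day 28, and who goes home on Day 70, is still ranked at 181.

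**2. Does another planned analysis recover the observed days?** No.

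- The worst-case, best-case and tipping-point analyses in 2.2.1.4 concern missing ranks.
- The log-rank analysis there is for full enteral feeding only.
- The twin analyses (2.2.1.5) reuse the ranks of 2.2.1.3.2.
- The per-protocol analysis (2.2.1.6) repeats the main method.
- Tie-breaking (2.2.1.7) is for NFE.

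**3. The plan's own sample size.** SAP 1.3.3 uses 8.0 v 6.6 days, SD 3.5, two-sided 5% and 85% power by t-test. The standardised effect is 1.4/3.5 = 0.4.

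n per group = 2(1.960 + 1.036)² × (3.5/1.4)² = 2 × 8.98 × 6.25 ≈ 112.2, so 113. The exact t calculation gives 113.2, so 114. The stated 115 is reproduced within tolerance. It applies to NFE; no power is stated for NRD.

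**4. Size of the effect on NRD (assumptions, not document figures)**

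- 115 per arm; unstratified Wilcoxon test standing in for van Elteren; two-sided 0.05; 10,000 trials per scenario.
- Effect of 0.4 SD, borrowed from the primary endpoint.
- Stay either normal (mean 45, SD 15 days) or lognormal (median 42, log-SD 0.35).
- NEC independent of underlying stay; NEC infants all discharged, after 0, 15 or 30 extra days.
- The literal rule places NEC infants at 181 or above, earlier NEC worse.

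Without NEC, power is 0.84. Ranges below cover both shapes and all three values for extra days.

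| NEC, placebo / active | Observed NRD kept | Literal 181 rule | Change (points) |
|---|---|---|---|
| 2% / 2% | 0.82–0.84 | 0.80–0.81 | −1 to −3 |
| 5% / 5% | 0.79–0.85 | about 0.76 | −3 to −8 |
| 10% / 10% | 0.74–0.85 | 0.66–0.67 | −7 to −18 |
| 10% / 5%, or 5% / 2.5% | 0.84–0.90 | 0.86–0.90 | −1 to +5 |
| 5% / 7.5% | 0.68–0.84 | about 0.61 | −7 to −23 |
| 5% / 10% | 0.56–0.83 | 0.44–0.46 | −11 to −39 |

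With identical arms and NEC at 5% or 10%, the literal rule rejects in 0.050–0.052 of trials.

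**5. Cross-checks.** A second model used 45 v 37 days, SD 20 (8/20 = 0.4), with 20% of NEC infants dying and survivors staying 20 days longer. Power with observed NRD kept v the literal rule was 83% v 79% at 3% NEC in both arms, 81% v 75% at 5% and 80% v 70% at 8%.

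Earlier-born infants plausibly have both more NEC and longer stays, so NEC was also correlated with underlying stay in this kind of model, with 10–25 extra days for survivors. At an assumed latent correlation of 0.6, the loss falls from about 3–4 to 1–2 points at 3% NEC, from 5–6 to 1–3 at 5%, and from 8–11 to 2–6 at 8%.

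**The case against.** The best defence is that the authors meant 181 to stand for not discharged by Day 180. The rule sits under a heading about missing ranks, and an infant discharged on Day 70 has no missing rank. It speaks of censoring, which is language for an unobserved event, and 181 is one day past the horizon. Section 1.3.3 gives the NEC and death ranks only to infants who miss the event being ranked. Subsection 2.2.1.3.1, which SAP 3.1 cites for multiple imputation, is not in the public text and may say more.

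This makes the intention uncertain but does not settle the text. The operative sentence is defined by having NEC, not by lacking a discharge date, and the only condition within reach concerns feeding.

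It can also be said that ranking NEC below a long stay is a legitimate composite, consistent with the primary endpoint. That stands as a possible choice, but neither the NRD objective nor its hypothesis declares it. The extension to 2.2.2 carries less weight, since those tests are exploratory.

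A reader might infer more than the documents support:

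- *That every NEC infant loses the observed day.* This holds only on the literal reading.
- *That NEC infants are tied.* They are ordered by time to NEC.
- *That the test no longer compares days to discharge.* Infants without NEC or death keep their observed days.
- *That power is necessarily lost.* The sign depends on the drug's effect on NEC, which the documents do not give.

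**Conclusion.** The point holds as a defect of specification. As written, the rule can replace an observed NRD at a confirmatory step. That conflicts with the hypothesis in SAP 2.2.1.2, with the reason Section 4 gives for the 180-day horizon, and with the limit in protocol 12.1.1 to infants not reaching NRD. At best the text is ambiguous.

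Validity under the null is not in question. What changes is what is estimated and, possibly, power at step 2. The losses of 1–3, 3–8 and 7–18 points at 2%, 5% and 10% NEC rest on an assumed 0.4 effect, equal NEC rates, and NEC independent of underlying stay. They shrink if NEC goes with longer stay, are about nil or a small gain if the drug halves NEC, and are larger if NEC is commoner on active. They show what could be at stake and do not forecast this trial. The correction should be made before unblinding.

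**What to change.** In SAP 2.2.1.3.2, state that an infant whose discharge or readiness is observed by Day 180 keeps the observed NRD, even if NEC occurred or death followed discharge. Use 181 only for NEC infants alive without discharge or readiness by Day 180, and 182 only for deaths before discharge or readiness. Add the same event-not-reached condition to the time-to-event endpoints in 2.2.2. Keep the all-NEC-at-181 ranking as a sensitivity analysis.

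If a composite is what the sponsor wants, declare it in the NRD definition and hypothesis, and make the observed-NRD ranking the sensitivity analysis. Either way, reconcile the text with SAP 1.3.3 and protocol 12.1.1, and list the change in Section 4.

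The cost is a few sentences and one extra analysis; the discharge and readiness days are already needed for the endpoint. The small downside is that NEC is no longer an automatic near-worst rank for NRD. It still counts through any longer observed stay and is reported under safety.
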